## 5.7. Safety [REDACTED]

Adverse events (AEs) will be collected throughout the study and coded using the Medical Dictionary for Regulatory Activities (MedDRA). Adverse events will be summarized based on the principle of treatment emergence.

A treatment-emergent adverse event is defined as 1) any adverse event that has onset on or after start of study drug infusion, or 2) any pre-existing condition that has worsened after start of study drug infusion. On-treatment events are treatment-emergent events that occurred within 3 days after end of study drug infusion. Similarly, on-treatment laboratory data are those from the samples taken from start of study drug infusion to 3 days after the end of study drug infusion. Handling of missing or partial date/time for adverse events and laboratory data is described in Section [5.1](#).

### 5.7.1 Adverse Events

The incidence of treatment-emergent adverse events will be summarized by actual treatment group and for the safety analysis set overall, by severity, and by relationship to study treatment.

For the analysis of AE incidence by severity, the occurrence of the AE with the greatest severity will be used, and a participant will be counted only once and only in the category of the greatest severity for each event.

For the analysis of AE incidence by relationship to study treatment, the occurrence of the AE with the strongest relationship to study treatment will be used and a participant is counted only once and only in the category of the strongest relationship to study treatment for each event.

AEs during on-treatment period will be provided for the safety analysis set of the Day 4 database and summarized for CSR in the Day 180 database.

- AEs during on-treatment period will be summarized by actual treatment group and
  - by system organ class (SOC) and preferred term (PT).
  - with  $\geq 5\%$  higher in incidence for BIIB093 combined compared to placebo by SOC and PT.
  - with  $\geq 5\%$  higher in incidence for BIIB093 combined or placebo by SOC and PT.
  - with  $\geq 5\%$  in incidence for BIIB093 combined or placebo by PT.
- Related AEs (see Section 15.2.2 of the protocol) during on-treatment period by SOC and PT will be summarized by treatment group.
- AEs and related adverse event during on-treatment period by maximum severity, SOC and PT will be summarized by actual treatment group, respectively.
- Serious adverse events (SAEs) and related SAEs during on-treatment period by SOC and PT will be summarized by actual treatment group, respectively.
- AEs leading to the following events by maximum severity, SOC and PT will be summarized by actual treatment group, respectively.
  - AEs leading to early termination of study drug infusion.
  - AEs leading to infusion interruption.

- AEs leading to infusion rate change.
- AEs leading to infusion dose reduction.

AEs during the study will be summarized for the safety analysis set when applicable:

- AEs and related AEs during the study by SOC and PT will be summarized by actual treatment group, respectively.
- AEs and related AEs during the study by maximum severity, SOC and PT will be summarized by actual treatment group, respectively.
- SAEs and related SAEs during the study SOC and PT will be summarized by actual treatment group, respectively.
- AEs leading to withdrawal from study by maximum severity, SOC and PT will be summarized by actual treatment group, respectively.

The following listings will be provided, when applicable:

- Listing of AEs during the study.
- Listing of SAEs during the study.
- Listing of AEs leading to early termination of study drug infusion.
- Listing of AEs leading to infusion interruption.
- Listing of AEs leading to rate change and dose reduction.
- Listing of AEs leading to withdrawal from study.

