4.5.1.2. Selection of 5 mg/day

In addition to 3 mg/day, this study will also evaluate a higher dose at 5 mg/day, on the basis of retrospective and exploratory exposure-response analyses, conducted by both Biogen and independent investigators, demonstrating increased efficacy of BIIB093 with higher exposures, as detailed below.

A retrospective analysis of Study 201, a pilot study of BIIB093 in LHI, dichotomized participants into low and high exposure cohorts. Analysis of efficacy data by exposure demonstrated improved mitigation of vasogenic edema (measured by T2 Flair MRI) with higher BIIB093 exposures (average concentration of 32 ng/mL) versus lower plasma levels (average concentration 16 ng/mL) [Kimberly 2014]. Notably, 25 ng/mL is the target concentration for 3 mg/day. Additionally, an exploratory analysis using data from Study 203 (pivotal Phase 2 LHI study) showed a consistent trend of higher BIIB093 exposure correlating with improved efficacy outcome (reduction of midline shift). A relationship between increasing BIIB093 exposure and decreasing matrix metalloprotease-9 (MMP-9) concentration was also observed, suggesting improved blood-brain- barrier integrity in the presence of higher BIIB093 drug exposure. Therefore, greater efficacy is anticipated for brain contusion at the higher dose of BIIB093.

The specific dose level at 5 mg/day was selected based on a totality of clinical safety (severe hypoglycemia) and pharmacodynamics (PD) data (blood glucose). Up to 10 mg/day has been previously evaluated in the first-in-human study in healthy participants (Study 101).

Symptomatic severe hypoglycemia, or BG < 55 mg/dL (~3.1 mmol/L), was observed in 6 mg/day and 10 mg/day cohorts, and 3 mg/day was the highest dose studied that did not result in severe hypoglycemia. Doses between 3 and 6 mg/day have not been evaluated clinically. No apparent exposure-response relationship between BIIB093 plasma concentration and BG level was observed. As such, safety results from Study 101 were used to inform the clinical concentration threshold for severe hypoglycemia, which was 75 ng/mL. PK simulations of the anticipated exposures at 5 mg/day (mean plasma concentration at steady state: 40 ng/mL, 95% CI: 13.4, 61.8) showed the maximum predicted BIIB093 plasma concentration would remain below the threshold where severe hypoglycemia was observed.

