### **3.2. Study Treatment**

All participants must be dosed within 10 hours of time of trauma/last known normal (LKN) and within 6 hours of hospital arrival. Dosing should be initiated within 1 hour of randomization and continue for 96 hours (4 days). Participants will receive study treatment (3 mg/day or 5 mg/day) or matching placebo administered as a 3-stage continuous infusion: a bolus IV dose (given over 2 minutes), followed by 2 different infusion rates (a rapid IV infusion for 6 hours followed by a slow IV infusion for the remaining 90 hours) for 96 hours total. Participants will be randomly assigned to 3 mg/day study treatment, 5 mg/day study treatment, 3 mg/day matching placebo, or 5 mg/day matching placebo in a 1:1:1:1 ratio, stratified based on baseline contusion volume per Investigator assessment of noncontrast computed tomography scan or site local radiologic assessment (3 to 10 mL or > 10 mL), baseline GCS (5 to 8, 9 to 12, or 13 to 15), age ( $\leq$  70 years old or > 70 years old), and region (North America [United States] or Rest of World).

By-treatment-group analysis will be displayed as:

- Placebo
- BIIB093 3 mg/day

- BIIB093 5 mg/day
- BIIB093 combined
- Total, if applicable

The treatment groups are defined as follows.

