### **3.2.2 Actual Treatment Group**

Actual treatment refers to the actual study drug received by a participant.

- Randomized participants who are dosed but never receive any BIIB093 during study treatment administration will be assigned to placebo group.
- Randomized participants who receive any BIIB093 will be assigned to BIIB093 3 mg/day group, if the IV dose during bolus  $< 0.17$  mg and the following IV infusion received by the participant  $< 11.31$  mg for Infusion 1 and  $< 13.525$  mg for Infusion 2; refer to Table 1 of the protocol.
- Randomized participants who receive any BIIB093 will be assigned to BIIB093 5 mg/day group, if the IV dose during bolus  $\geq 0.17$  mg or the following IV infusion received by the participant  $\geq 11.31$  mg for Infusion 1 or  $\geq 13.525$  mg for Infusion 2.
- Randomized participants who never receive any study drug (neither BIIB093 nor the matching placebo) will have missing actual treatment group and will be excluded in the analysis by actual treatment group.

Study results for safety (adverse events, serious adverse events, laboratory, vital signs, liver function test, electrocardiogram [ECG]), extent of exposure, [REDACTED] will be analyzed and presented by actual treatment group.

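### The SAP's threshold adverse-event tables select terms on the two doses combined, so an excess confined to 5 mg/day must reach 10 points to enter a 5-point excess table

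*SAP*

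**What the plan says.** SAP 5.7.1 opens its on-treatment list with "AEs during on-treatment period will be summarized by actual treatment group and" then names the displays. The first, by system organ class and preferred term, has no threshold. Three further displays select terms with a 5% rule:

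- at least 5% "higher in incidence for BIIB093 combined compared to placebo by SOC and PT";
- at least 5% "higher in incidence for BIIB093 combined or placebo by SOC and PT";
- at least 5% "in incidence for BIIB093 combined or placebo by PT".

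The first two are excess rules and the third is a frequency rule. None applies the threshold to 3 mg/day or 5 mg/day alone.

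The doses are nonetheless shown separately. SAP 3.2 introduces its column list with "By-treatment-group analysis will be displayed as" and gives placebo, each dose, the doses combined and, where applicable, a total. SAP 3.2.2 says that safety results "will be analyzed and presented by actual treatment group", and those groups keep 3 and 5 mg/day apart.

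On prior experience, Protocol 4.5.1.2 states: "Doses between 3 and 6 mg/day have not been evaluated clinically". It adds that 3 mg/day was the highest dose studied without severe hypoglycemia, which was seen at 6 and 10 mg/day in the first-in-human study. Protocol 4.5.1.2 also says that the 5 mg/day exposure figures come from simulation.

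**The concern.** The 3 mg/day dose has been used in the Phase 2 stroke studies, while 5 mg/day has no clinical record before this trial. A main safety question is therefore what the higher dose adds. Under "5 mg/day matching placebo in a 1:1:1:1 ratio" the 5 mg/day arm is planned to be half of the combined active group, so pooling dilutes anything specific to it before the 5% rule is applied.

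For efficacy, SAP 5.6.1 estimates each dose against placebo with confidence intervals, and SAP 5.6.3 draws survival curves by dose. The adverse-event selection rules have no such step. At stake is whether an unanticipated event concentrated at 5 mg/day is picked out by a rule fixed in advance, or depends on someone noticing it in a long table after unblinding.

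**Working it through.** **Inputs from the documents.** 40 participants per randomized arm, hence 40 per dose, 80 on active and 80 on placebo (SAP 2.3); 5% threshold (SAP 5.7.1).

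**Assumptions.** 5% means percentage points of observed incidence (the SAP does not say); actual dose groups are equal; event rates are illustrative, because the documents give none.

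**The plan's own figure.** The SAP gives no sensitivity for these tables. Its one design calculation, about 90% power for 15 mL with SD 29 mL and 80 per group, reproduces: 15 / (29 × √(2/80)) = 3.27; 3.27 − 1.96 = 1.31; Φ(1.31) = 0.905 (0.902 by noncentral t). The group sizes are therefore taken as stated.

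**Dilution.** With e3 and e5 the excess of each dose over placebo,

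combined excess = (n3 × e3 + n5 × e5) / (n3 + n5).

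With n3 = n5 = 40 and e3 = 0 this is e5 / 2. An excess of 5 points at 5 mg/day becomes 2.5, 9 becomes 4.5 and 10 becomes 5.0, so 10 points are needed whatever the placebo rate. Sensitivity of that figure:

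- Group sizes 45 (3 mg/day) and 35 (5 mg/day): 5 × 80 / 35 = 11.4 points. Sizes 35 and 45: 5 × 80 / 45 = 8.9 points.
- 3 mg/day 2.5 points above placebo: 10 − 2.5 = 7.5 points. 2.5 points below: 12.5 points.

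**Selection probabilities.** Let X5, X3 and Y be the participants with the event on 5 mg/day, 3 mg/day and placebo. The combined excess rule is met when X5 + X3 − Y ≥ 4 (4/80 = 5 points). A single-dose rule is met when 2·X − Y ≥ 4. Exact binomial enumeration gives:

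| True rates: 5 mg / 3 mg / placebo | Combined (current rule) | 5 mg/day alone | Combined or 5 mg/day | Any of three |
|---|---|---|---|---|
| 15% / 5% / 5% | 0.557 | 0.818 | 0.825 | 0.833 |
| 10% / 5% / 5% | 0.307 | 0.530 | 0.549 | 0.578 |
| 5% / 5% / 5% | 0.100 | 0.148 | 0.180 | 0.260 |
| 10% / 10% / 10% | 0.177 | 0.221 | 0.271 | 0.366 |

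In the first row, 5 mg/day meets the 5-point rule while the combined group does not in 0.825 − 0.557 = 0.268 of trials. For a true 10-point excess at 5 mg/day only, placebo rates from 2% to 10% give 0.57 to 0.55 for the combined rule and 0.85 to 0.78 for 5 mg/day alone.

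**Frequency table.** An event in 3/40 on 5 mg/day (7.5%) and in nobody else is 3/80 = 3.75% combined and 0% on placebo. It misses the 5% incidence table as well as both excess tables.

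**The case against.** A reader might infer that a harm specific to 5 mg/day would be missed or left unreported. The documents do not support that. SAP 5.7.1 requires the unfiltered on-treatment table, and tables of serious events, severity and events leading to infusion changes, by actual treatment group. Nor does the SAP say that the threshold tables decide which events count as more common on drug, or that dose selection for Phase 3 rests on them.

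A reader might also think that hypoglycemia, the risk behind the caution about 5 mg/day, passes through these filters. It does not. It is an event of special interest upgraded to a serious event (Protocol 15.3.2), summarized by actual treatment group without a threshold (SAP 5.7.2), and SAP 5.7.4 adds counts below 55, 80 and 120 mg/dL. The data monitoring committee reviews data every 3 to 5 months (SAP 4.4).

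The frequency table also catches much of what the excess tables leave out. With 6/40 on 5 mg/day, 2/40 on 3 mg/day and 5/80 on placebo, the combined rate is 8/80 = 10% against 6.25%. The 3.75-point difference fails the excess rule, but the term enters the frequency table, where 5 mg/day has its own column. At true rates of 15%/5%/5% a term enters that table with probability 0.986. The chance that 5 mg/day is at least 5 points above placebo while the term is in neither the combined-excess nor the frequency table is 0.003; at 12%/2%/2% it is 0.067.

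Finally, selecting terms on the pooled arm matches the pooled primary comparison, and with 40 per dose two participants make 5 points, so single-dose screens are noisy.

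All of this stands, and it keeps the severity low. It does not answer the narrower point: the frequency table does not mark an event as an excess, and no prespecified rule responds to 5 mg/day alone.

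**Conclusion.** The point holds as a gap in prespecified flagging, not in reporting. The two excess tables need a 10-point excess at 5 mg/day when the effect is confined to that dose. At assumed rates of 15%/5%/5% they select the term with probability 0.56, where a rule that also screens 5 mg/day would reach 0.83. A rare event seen only on 5 mg/day can fall out of all three threshold tables.

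The 10-point figure rests on equal actual dose groups, 3 mg/day at the placebo rate and 5% meaning percentage points; the probabilities also rest on assumed event rates. The practical effect is limited to unanticipated events outside the hypoglycemia, glucose and serious-event summaries. Severity: CONSIDER.

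**What to change.** In SAP 5.7.1, extend the selection criteria of the three threshold tables so that a term enters if the combined group or BIIB093 5 mg/day meets the 5% rule, with 3 mg/day as an optional third trigger. Keep placebo as a trigger where it already is one, and state that 5% means percentage points.

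The columns already exist, so this takes SAP wording and one filter condition, with no new data. The downside is more chance entries. For an event at 5% in all arms, the probability of entering the excess-over-placebo table rises from 0.10 to 0.18 with 5 mg/day added, or to 0.26 with all three columns. At 10% in all arms the any-of-three figure is 0.37 against 0.18 now. Most of the gain comes from adding 5 mg/day: the third trigger lifts selection at 15%/5%/5% only from 0.825 to 0.833. The tables are descriptive and carry no tests, so the extra entries are tolerable if a footnote states the selection rule.

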### **5.7.2 Adverse Events of Special Interest (AESI)**

The adverse event of special interest (AESI) categories may include but are not limited to hypoglycemia (BG < 55 mg/dl).

- AESI during on-treatment and during the study will be summarized by actual treatment group for the safety analysis set, respectively.

In addition, the following listings will be provided:

- Listing of adverse events of special interest during the study.
- Listing of hypoglycemia events during the study.
- Listing of adverse events for participants with any hypoglycemia events.

### **5.7.3 Death**

All-cause deaths and deaths by the neurological criteria will be summarized for all randomized participants.

- Number (%) of deaths during on-treatment will be summarized by actual treatment group.
- Number (%) of deaths before Discharge, Day 30, Day 90 and Day 180 will be summarized by actual treatment group.

- Listing of deaths during the study will be provided, including timing of the death relative to study treatment and the investigator assessment of the cause of death.

#### **5.7.4 Clinical Laboratory Results**

Clinical laboratory evaluations include hematology and blood chemistry will be summarized by actual treatment group for the safety analysis set.

Hematology, including but not limited to the following parameters:

- White blood cells (leukocytes)
- Absolute neutrophil counts
- Red blood cells
- Hemoglobin
- Hematocrit
- Platelet count

Blood chemistry, including but not limited to the following parameters:

- Liver: alanine aminotransferase (ALT), aspartate aminotransferase (AST), alkaline phosphatase (ALP), total bilirubin, and direct bilirubin
- Renal: blood urea nitrogen (BUN) and creatinine
- Electrolytes: sodium, potassium, and bicarbonate
- Other: glucose, calcium, phosphorus and albumin

#### **Shift Analyses**

Laboratory abnormalities will be summarized with shift tables. Tables will present changes relative to each parameter's normal ranges. Each participant's hematology and blood chemistry values will be flagged as "low", "normal", or "high" relative to the normal ranges of the local laboratory or as "unknown" if no result is available.

Shifts from baseline to high/low status for hematology and blood chemistry parameters will be presented. In each summary, the denominator for the percentage is the number of participants at risk for the shift. The number at risk for shift to low is the number of participants whose baseline value was not low and who had at least one post-baseline value. The number at risk for shift to high is the number of participants whose baseline value was not high and who had at least one post-baseline value. Participants will be counted only once for each parameter and each type of shift regardless of how many post-dosing assessments had that type of shift. Participants with shift to low or high will be listed by laboratory parameter and shift type.

#### **Potentially Clinically Significant Laboratory Abnormalities Analyses**

For hematology and blood chemistry, the number of participants with potentially clinically significant laboratory abnormalities post-baseline will be summarized for the parameters provided in [Table 4](#). Participants need to have at least one post-baseline evaluation and a baseline

value not potentially clinically significant (including missing) in order to be included in the analysis.

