4.3.3. Benefit/Risk

BIIB093 has been shown to potentially reduce mortality associated with LHI, reducing brain edema, and improving functional outcomes.

BIIB093 given intravenously in a 3-stage dosing regimen over 72 hours was generally well tolerated in the population of participants with LHI and TBI. The only adverse drug reaction identified was hypoglycemia, which can be mitigated by frequent blood glucose (BG) measurement and dose adjustment. The safety profile of BIIB093 observed in completed studies in participant with LHI and TBI is detailed in the Investigator's Brochure. Based on the safety profile and observed benefit in Phase 2 studies of BIIB093 for treatment of LHI and TBI, Biogen

CONFIDENTIAL

The information contained herein may not be used, disclosed, or published without the written consent of
Biogen MA Inc.

considers that the benefit/risk profile of BIIB093 remains positive and supports the continued development of BIIB093 for the treatment of patients with LHI and brain contusion.

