15. Patients in whom a peripheral IV line cannot be placed.
16. Mentally incompetent (prior to trauma) patients and wards of the state, if known.

Medical History

17. Known allergy to BIIB093 or another sulfonylurea drug or any of the components of the formulated BIIB093 or matching placebo.
18. Participants who are known to have taken oral glibenclamide within the past 10 hours.
19. A clinically significant severe form of renal or hepatic disorder in the Investigator's opinion from the patient's history (e.g., dialysis), if known.
20. Known history of G6PD deficiency.
21. Clinically significant hypoglycemia in the Investigator's opinion based on known medical history or screening laboratory assessments (i.e., screening BG < 70 mg/dL [~3.9 mmol/L]).
22. Patients who have or have ever had diabetic ketoacidosis or diabetic coma/precoma, if known.

CONFIDENTIAL

The information contained herein may not be used, disclosed, or published without the written consent of Biogen MA Inc.

23. Uncontrolled hypertension (defined as systolic blood pressure > 200 mmHg continuously for over 60 minutes).
24. Hemodynamic instability (use of inotrope or vasopressor therapy or resuscitation requiring > 6 L crystalloid or colloid).

Note: transient vasopressor used to support blood pressure during specific procedures (e.g., intubation or hypotension associated with sedation/analgesics) is permitted.
25. Diabetes controlled with sulfonylurea medication, if known.
26. Life-threatening or nonsurvivable polytrauma, per Investigator's judgment.
27. Cardiopulmonary resuscitation required at any point after injury or suspected anoxic brain injury based on clinical judgment.
28. History, within the past 6 months, of decompensated congestive heart failure (New York Heart Association heart failure Class III or IV – Class III: marked limitation in activity due to symptoms, even during less-than-ordinary activity, e.g., walking short distances [20 to 100 m]; class IV: severe limitations, experiences symptoms even while at rest. Mostly bedbound patients), if known.
29. Acute Coronary Syndrome within 3 months, if known.
30. Likely to be moved to CMO in the next 24 to 96 hours, in the opinion of the Investigator.

Medications

Every effort should be made to determine if patient was taking any of the following medications prior to randomization:

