## **3.3. Study Periods**

### **Pretreatment Period**

The pretreatment period begins at the admission to hospital at the screening visit until start time of study drug infusion (Hour 0).

Measurements taken before the time of study drug infusion at Hour 0 are considered pretreatment for all data domains. If the time of measurement is missing, measurements taken on

Day 1 are considered pretreatment for the following data domains: demography, disease history, ECG, human genotyping, laboratory test results, medical history, physical examinations, participant status, and vital signs.

Baseline value is defined as the last non-missing value before the time of study drug infusion (Hour 0) or prior to or on Day 1 if the time of study drug infusion is missing.

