**Table 4. Criteria to Potentially Clinically Significant (PCS) Laboratory Abnormalities**

Clinical Laboratory Outlier Criteria		
Parameter name	PCS Low	PCS High
HEMATOLOGY		
White blood cells	$< 3.0 \times 10^9/\text{L}$	$> 16 \times 10^9/\text{L}$
Neutrophils	$< 1.5 \times 10^9/\text{L}$	$> 13.5 \times 10^9/\text{L}$
Red blood cells	$\leq 3.5 \times 10^{12}/\text{L}$	$\geq 6.4 \times 10^{12}/\text{L}$
Hemoglobin - Females	$\leq 95 \text{ g/L}$	$\geq 175 \text{ g/L}$
Hemoglobin - Males	$\leq 115 \text{ g/L}$	$\geq 190 \text{ g/L}$
Hematocrit - Females	$\leq 32\%$	$\geq 54\%$
Hematocrit - Males	$\leq 37\%$	$\geq 60\%$
Platelet count	$\leq 75 \times 10^9/\text{L}$	$\geq 700 \times 10^9/\text{L}$
BLOOD CHEMISTRY		
Alanine aminotransferase (ALT)	N/A	$> 3 \times \text{ULN}$
Aspartate aminotransferase (AST)	N/A	$> 3 \times \text{ULN}$
Alkaline phosphatase (ALP)	N/A	$> 3 \times \text{ULN}$
Total bilirubin	N/A	$> 1.5 \times \text{ULN}$
Blood urea nitrogen (BUN)	N/A	$\geq 10.7 \text{ mmol/L}$
Creatinine	N/A	$\geq 176.8 \mu\text{mol/L}$
Sodium	$\leq 126 \text{ mmol/L}$	$\geq 156 \text{ mmol/L}$
Potassium	$\leq 3 \text{ mmol/L}$	$\geq 6 \text{ mmol/L}$
Bicarbonate	$\leq 16 \text{ mmol/L}$	$\geq 35 \text{ mmol/L}$
Glucose	$\leq 2.2 \text{ mmol/L}$	$\geq 9.7 \text{ mmol/L}$

Clinical Laboratory Outlier Criteria		
Parameter name	PCS Low	PCS High
Calcium	$\leq 2$ mmol/L	$\geq 3$ mmol/L
Phosphorus	$\leq 0.6$ mmol/L	$\geq 1.7$ mmol/L
Albumin	$\leq 25$ g/L	$\geq 625$ g/L
ULN = upper limit of normal		

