### Analysis of Blood Glucose

The blood glucose from local laboratory are collected at screening, Hours 0-12, Hour 24, Hour 48, Hour 72, Hour 96 and Day 7 with the normal ranges. Additionally, the Point-of-Care (POC) blood glucose is collected pre-dose, hourly up to Hour 96 without normal ranges. The normal range for POC blood glucose data are assigned as between 70 mg/dL and 139 mg/dL, according to the reference range recommended by the American Diabetes Association for random blood glucose measurements. For all analyses, the two sources of data (local laboratory and POC) will be combined and analyzed together.

Summary of lowest post-baseline value of blood glucose will be provided. The number (%) of participants with post-baseline blood glucose abnormalities ( $<55$  mg/dL,  $<80$  mg/dL,  $<120$  mg/dL) will be summarized by actual treatment group. Blood glucose values for participants with post-baseline blood glucose  $<55$  mg/dL will be listed.

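### The SAP's at-risk rule for potentially clinically significant (PCS) laboratory values names no direction, so as written a PCS High baseline removes a participant from the PCS Low count, and the reverse

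*SAP*

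**What the plan says.** SAP 5.7.4, under Potentially Clinically Significant Laboratory Abnormalities Analyses, sets two conditions for entering the count of post-baseline PCS values: at least one post-baseline evaluation, and a baseline "value not potentially clinically significant (including missing) in order to be included in the analysis". Nothing in that paragraph ties the baseline condition to the direction being counted.

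SAP Table 4 then has a PCS Low column and a PCS High column. For glucose the limits are 2.2 mmol/L or below and 9.7 mmol/L or above.

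The Shift Analyses paragraph, just before the PCS rule, works differently: "The number at risk for shift to low is the number of participants whose baseline value was not low". It gives the matching definition for shifts to high. Both also require a post-baseline value.

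Three other places bear on glucose:

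- Protocol 4.3.3 states: "The only adverse drug reaction identified was hypoglycemia".
- Protocol 8.2 (criterion 21) excludes clinically significant hypoglycemia, specified as "screening BG < 70 mg/dL". No criterion sets an upper limit on glucose.
- SAP 5.7.4, Analysis of Blood Glucose, says that "the two sources of data (local laboratory and POC) will be combined and analyzed together". It separately plans a count, described as "The number (%) of participants with post-baseline blood glucose abnormalities", at cut-offs of 55, 80 and 120 mg/dL, with no baseline condition stated.

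**The concern.** An at-risk set for a low value should leave out only people who already had a low value. A rule that also leaves out people who started high conditions on something irrelevant to the event, and it shrinks both numerator and denominator.

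Glucose is where this matters most. Low glucose is the one adverse reaction the protocol identifies. Eligibility already screens out low values, so for glucose the baseline rule would remove almost only participants who started high. In the visible text, the PCS table is also the only tabulated count at about 40 mg/dL, because the dedicated glucose summary stops at 55 mg/dL.

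The same wording governs every two-sided parameter in Table 4. A leukocyte or neutrophil count above the PCS High limit at entry removes the participant from the PCS Low count. For parameters other than glucose, the visible text has no second count against fixed clinical limits.

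**Working it through.** The plan states no figure to reproduce here. The check is a reading of the rule, a unit conversion and an illustration of size.

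**1. Convert the limits.** Inputs: glucose limits from SAP Table 4; factor 18.016 mg/dL per mmol/L. The factor agrees with the protocol's own rounded pairs (70 / 18.016 = 3.89, printed as 3.9; 180 / 18.016 = 9.99, printed as 10).

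- PCS Low: 2.2 × 18.016 = 39.6 mg/dL.
- PCS High: 9.7 × 18.016 = 174.8 mg/dL.

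The high limit lies inside the on-infusion range of 140 to below 180 mg/dL in protocol 11.4.1.1.1 and Table 5, so it is not an extreme value in this trial.

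**2. Apply the rules to two constructed records.** Both have a lowest on-infusion value of 2.0 mmol/L (36.0 mg/dL).

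| Baseline glucose | PCS rule, read literally | Direction-specific rule | Shift to low | Count below 55 mg/dL |
|---|---|---|---|---|
| 7.0 mmol/L (126.1 mg/dL) | counted | counted | counted | counted |
| 10.5 mmol/L (189.2 mg/dL) | excluded | counted | counted | counted |

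Only the literal PCS rule treats the two records differently.

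**3. Scope in Table 4.** Thirteen of the 19 parameters have both limits: leukocytes, neutrophils, red cells, hemoglobin, hematocrit, platelets, sodium, potassium, bicarbonate, glucose, calcium, phosphorus and albumin. The six with only a high limit (ALT, AST, ALP, total bilirubin, BUN, creatinine) are unaffected.

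**4. Possible number affected.** The documents give no baseline glucose distribution. *Assumption:* normal baselines with the means and SDs below, chosen only to show a range. Share removed = P(Z ≥ (174.8 − mean) / SD), applied to the planned 160.

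| Assumed mean, SD (mg/dL) | z | Share removed | Of 160 |
|---|---|---|---|
| 130, 35 | 1.28 | 0.10 | 16 |
| 140, 40 | 0.87 | 0.19 | 31 |
| 150, 45 | 0.55 | 0.29 | 47 |
| 160, 50 | 0.30 | 0.38 | 61 |

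These are participants not assessed in one table, across all arms. They are not missed events.

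**5. Effect on expected cases.** Take the pooled active group of 80 and *assume* a PCS Low risk r that does not depend on baseline glucose. The expected count is 80r under the direction-specific rule and 80r(1 − h) under the literal rule, where h is the share removed.

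| Assumed r | Direction-specific | Literal, h = 0.10 | Literal, h = 0.38 |
|---|---|---|---|
| 0.02 | 1.6 | 1.44 | 0.99 |
| 0.05 | 4.0 | 3.6 | 2.48 |
| 0.10 | 8.0 | 7.2 | 4.96 |

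With equal risk the expected proportion stays at r, because numerator and denominator shrink together. The proportion is distorted only if participants who start high have a different risk, and the documents do not show whether they do.

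**The case against.** The strongest reply is that the sentence never says a PCS value in either direction excludes. Table 4 has separate Low and High columns and the preceding paragraph defines risk by direction, so a programmer may well apply the PCS rule column by column. That is a fair account of what might happen. It does not change what the sentence says, and a SAP should not leave a denominator to inference when the neighbouring rule is explicit.

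The second reply is that low glucose is well covered elsewhere. This stands. Any value at or below 39.6 mg/dL is also below 55 mg/dL, so it enters the Analysis of Blood Glucose count and listing. If confirmed, it is an adverse event of special interest, upgraded to serious under protocol 15.3.2. The shift tables keep participants with high baselines, and individual laboratory values are listed.

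The third reply is that baseline precedes dosing (SAP 3.3) and allocation is randomized and blinded, so the restriction is not expected to favour either arm, and no test or decision uses this table. This also stands.

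Two stronger readings are tempting. A reader might infer that hypoglycemia cannot be counted in participants who arrive with high glucose; the displays just listed show otherwise. A reader might also expect the PCS table and the 55 mg/dL table to contradict each other because of this rule. Their cut-offs differ (about 40 and 55 mg/dL), so their counts can differ under any baseline rule.

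**Conclusion.** Wrong as written, and minor. The PCS at-risk rule, taken literally, excludes participants from the count in one direction because of a baseline abnormality in the other. It conflicts with the shift-table rule in the same section, and no other passage corrects it. PCS incidence is therefore incomplete for the 13 two-sided parameters.

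The consequence is limited to a descriptive table. Hypoglycemia is not lost from the safety report and no between-arm bias is expected. For glucose, the 10% to 38% of 160 (about 16 to 61 participants) rests entirely on assumed normal baselines; the true share is unknown and could lie outside that range. Reading those figures as missed hypoglycemia events would be a mistake. The number of PCS Low events affected cannot be estimated from the documents.

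**What to change.** In SAP 5.7.4, replace the inclusion sentence with:

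> For PCS Low, participants with a baseline value that is not PCS Low (including missing) and at least one post-baseline value are included; for PCS High, participants with a baseline value that is not PCS High (including missing) and at least one post-baseline value are included.

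This brings the PCS rule into line with the shift-table rule and corrects every two-sided parameter in Table 4 at once. It costs one sentence in the SAP and a small change to the table program, with no new data, and is best made before database lock.
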